### 4.3 Secondary variables

#### 4.3.1 Efficacy

- Estimated PV (by Kaplan-Hakim's formula, see chapter 7.2) and measured PV (assessed by FAST methodology) on days 1 and 3
- Estimated TBV (by Nadler's formula, see chapter 7.2) and measured TBV (mTBV: calculated from mPV and measured hematocrit, see chapter 7.2) on days 1 and 3
- Estimated GFR (CKD-EPI formula, sMDRD, Cystatin C formula, and Creatinine-Cystatin C formula, see chapter 7.2) and measured GFR (assessed by FAST methodology) on days 1 and 3 in heart failure patients undergoing active fluid management
- Development of AKI within 72 hours after day 1 and 48 hours after day 3 respectively
- Current level and level within last 24 hours of well-being, dyspnea, dizziness, nausea reported on day 1 and day 3
- Subjectively reported symptoms (PGA, dyspnea, dizziness, nausea) determined using patient symptom assessment sheets within the following 24 and 48 hours on day 1 and following 24 and 48 hours on day 3
- Low-output complications within the next 24 and 48 hours (e. g. subjectively reported dizziness/nausea, PGA, hypotension (Systolic <100, diastolic <60mmHg), need for iv-fluid therapy) at day 1 and within the next 24 and 48 hours at day 3
- Risk of being refractory to diuretic therapy (e. g. require dosage increases of furosemide/torsemide, require ultrafiltration/RRT within the next 24-48 hours, fail to improve subjectively in PGA and dyspnea scales) within 24 and 48 hours on day 1 and day 3

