To evaluate whether patients with a high mPVS ( $> +10\%$ ) or a high mTBVS ( $> +10\%$ ) on day 1 and/or day 3 are at risk of being refractory to diuretic therapy (defined as any dosage increases of furosemide i.v. dose equivalent, adding thiazide after day 1, require ultrafiltration/RRT within the next 24-48 hours, fail to improve subjectively in PGA and dyspnea scales, fail of mean weight loss during the study period Day 1-Day 5 of at least 0,5 kg/d) logistic regression models using mPV and mTBV as independent variables will be used.

To evaluate whether the changes of ePV (using relative and absolute change as well as the Strauss' formula) and eTBV (using relative and absolute change) from day 1 to day 3 adequately reflects the changes of mPV and mTBV Bland-Altman plots will be generated. These plots will be analysed exploratory, since no appropriate values for limits of agreements are available. The amount of values within 10% and within 30% of the measured values will also be determined. In addition, the diagnostic test accuracy including 95% confidence interval as proposed by Obuchowski will be calculated.

To evaluate whether the change of mPV and mTBV and changes of mPVS and mTBVS from day 1 to day 3 as well as the mPVS and mTBVS on Day 1 and Day 3 is predictive of the remaining length of stay at the given day (i.e. remaining length of stay starting with day 1 or with day 3), dialysis/ultrafiltration requirement, or rehospitalization within 30 days, or mortality, linear (remaining length of stay), logistic (dialysis/ultrafiltration, rehospitalization within 30 days) or Cox-regression models (mortality) will be utilized using changes of mPV and mTBV from day 1 to day 3 (first model), changes of mPVS and mTBVS from day 1 to day 3 (second model), and mPVS and mTBVS at day 1 (third model) and day 3 (fourth model) as independent variables.

To evaluate whether the percentage changes of mGFR from day 1 to day 3 ( $< 0$  vs.  $\geq 0$ ; continuous) predicts the percentage changes of eGFR from day 2 to day 4 (CKD-EPI formula only;  $< 0$  vs.  $\geq 0$ ; continuous), a logistic as well as a linear regression model will be used.

The same will be done to investigate the changes in eGFR from day 1 to day 3 (all formulas) as the dependent variable. Further, exploratory Bland-Altman plots without predefined limits of agreement will be created.

To evaluate whether patients with a high PVS or TBVS on Day 1 ( $> +10\%$ ) and a decreasing PVS

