or TBVS between Day 1 and 3 had significantly different percentage change of mGFR between Day 1 and Day 3 compared to patients with a high PVS or TBVS and an increasing PVS between Day 1 and 3, t-Tests or Mann-Whitney-U-tests will be used depending on the distribution of the values.

To evaluate whether Patients with a low PVS or TBVS on Day 1 (<-10%) and an increasing PVS or TBVS between Day 1 and 3 had significantly different percentage change of mGFR between Day 1 and Day 3 compared to patients with a low PVS or BCS and a decreasing PVS between Day 1 and 3, t-Tests or Mann-Whitney-U-tests will be used depending on the distribution of the values.

To evaluate whether patients with an improving (i.e. increasing) mGFR from day 1 to day 3 differ significantly from patients with a worsening (i.e. decreasing) mGFR regarding baseline characteristics (see chapter 4.1), mPVS, mTBVS, ePVS, eTBVS, and remaining length of stay appropriate tests depending on the distribution will be used (t-Test or Mann-Whitney-U-test for continuous variables and chi-square tests or Fisher-Boschloo-tests for categorical variables).

To evaluate whether disagreement between the physicians response to the question what they thought the intravascular volume of the patient was doing (increasing, decreasing, no change, treating physicians assessment Day 3) and the direction of measured change in TBVS is associated with a longer remaining length of stay, a t-test or Mann-Whitney-U-test depending on the distribution will be used. A measured change in TBVS of more than 5% between Day 1 and 3 was determined as a significant change.

To evaluate (by an adjudication committee) whether clinical decision making would have been affected by adding FAST GFR and PV measurements to clinical routine, the following questions were to be answered:

- How would you alter the intensity of Diuretic Therapy given on Day 1 and Day 3?
- How would you alter the intensity of RAASI Therapy given Day 1 and Day 3?  
How would you alter the intensity of Beta Blocker Therapy given Day 1 and Day 3?
- How would you alter the intensity of other GDMT given Day 1 and Day 3?

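### The arms of the two mGFR-change comparisons in SAP 7.7.1 are not mutually exclusive as written, because one arm is defined on PVS or TBVS and the other on PVS alone

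*SAP*

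**What the plan says.** Late in SAP 7.7.1 there are two group comparisons of the percentage change in mGFR between Day 1 and Day 3.

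- **High comparison.** Entry is for "patients with a high PVS or TBVS on Day 1", with a cutoff of +10%. The first arm needs a falling PVS, and the sentence continues "or TBVS between Day 1 and 3 had significantly different percentage change of mGFR", so a fall in either index qualifies. This arm is "compared to patients with a high PVS or TBVS and an increasing PVS between Day 1 and 3".
- **Low comparison.** Entry is low PVS or TBVS on Day 1, with a cutoff of -10%. The first arm is defined by "and an increasing PVS or TBVS between Day 1 and 3". It is "compared to patients with a low PVS or BCS and a decreasing PVS between Day 1 and 3". BCS appears neither in the SAP abbreviation list nor among the derived parameters in 7.2.

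For both, "t-Tests or Mann-Whitney-U-tests will be used depending on the distribution of the values". No rule says which index governs when PVS and TBVS disagree, either in Day 1 level or in direction. SAP 7.2 and 8 do not supply one.

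**The concern.** A two-sample test assumes that each patient contributes to one arm only. Here the first arm is selected on either index and the second on PVS alone. A patient whose two indices move in opposite directions can therefore be counted twice. The opposite discordance is treated differently: in the high comparison, a patient with falling PVS and rising TBVS goes only to the first arm. The contrast between falling and rising volume is then not made on one variable. Two programmers working from this text could build different groups and report different p-values for the same question.

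A second ambiguity lies in the entry condition. Because it also reads PVS or TBVS, a patient who is high on one index and low on the other on Day 1 qualifies for both the high and the low comparison.

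**Working it through.** The plan gives no power, sample size or alpha for these comparisons, so there is no figure to reproduce. The check is set logic with the SAP 7.2 formulas.

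**Inputs (SAP 7.2)**
- mTBV = mPV / (1 - Hct); SAP 4.3.1 has the same: "mTBV: calculated from mPV and measured hematocrit".
- iPV = 39 mL/kg (men) or 40 mL/kg (women) × weight.
- iTBV = 70 / sqrt(BMI/22) mL/kg × weight.
- Status = (measured - ideal) / ideal.
- Both ideal volumes use the lowest weight of Days 1 to 5, so they are constant within a patient. The direction of PVS is the direction of mPV; the direction of TBVS is the direction of mPV / (1 - Hct).

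**Condition for being in both high arms.** PVS up and TBVS down requires

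1 < mPV3/mPV1 < (1 - Hct3)/(1 - Hct1).

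From a Day 1 hematocrit of 40%, a fall of 1, 2 or 3 points gives upper limits of 0.61/0.60, 0.62/0.60 and 0.63/0.60. Any rise in mPV below 1.7%, 3.3% or 5.0% then puts the patient in both arms. The low arms share patients with PVS down and TBVS up, reading BCS as TBVS.

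**Worked patients.** Man, 80 kg, 1.75 m, BMI 26.1: iPV = 39 × 80 = 3120 mL; iTBV = 5139 mL.

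| | Day | mPV (mL) | Hct | mTBV (mL) | PVS | TBVS |
|---|---|---|---|---|---|---|
| High | 1 | 3600 | 40% | 6000 | +15.4% | +16.8% |
| High | 3 | 3650 | 37% | 5794 | +17.0% (up) | +12.7% (down) |
| Low | 1 | 2700 | 36% | 4219 | -13.5% | -17.9% |
| Low | 3 | 2650 | 39% | 4344 | -15.1% (down) | -15.5% (up) |

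Each patient meets both arm definitions of his comparison.

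**What the overlap depends on.** If the Day 1 hematocrit were reused on Day 3, the Day 3 TBVS in the high example would be +18.4%, moving with PVS, and there would be no overlap. The documents conflict here. SAP 4.3.2 says hematocrit is collected on Day 1 only. Protocol Table 7 (sections 4.4 and 7.4.4) collects it on Days 1 and 3. SAP 4.3.1 plans mTBV on both days, the Strauss formula in 7.2 needs two hematocrits, and SAP 5.2 plots a hematocrit series per patient.

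**Size under assumptions.** The documents give no spreads. Assumed: mean PV change -5% to +5%, SD 8% to 12%, Day 1 hematocrit 38%, SD of hematocrit change 1 to 3 points, correlation 0 or -0.5. By simulation, about 1% to 10% of eligible patients fall in both arms (similar for high and low), and 2% to 36% of the second high arm is also in the first. If all 50 patients were eligible for one comparison, that is 0.5 to 5 patients (50 × 0.01 to 50 × 0.10). Fewer will be eligible.

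**Effect on the test.** With arm sizes n1 and n2 sharing k patients, the true variance of the mean difference relative to what the t-test assumes is 1 - 2k/(n1 + n2). For an illustrative 15 versus 10:

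| Shared k | Variance ratio | Rejection rate at nominal 5%, no true difference (simulated) |
|---|---|---|
| 0 | 1.00 | 4.8% |
| 2 | 1 - 4/25 = 0.84 | 3.2% |
| 4 | 1 - 8/25 = 0.68 | 1.7% |

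**High and low on Day 1.** Man, 110 kg, 1.72 m, mPV 3800 mL, Hct 45%: PVS = (3800 - 4290)/4290 = -11.4%; TBVS = (6909 - 5923)/5923 = +16.7%. Man, 70 kg, 1.78 m, mPV 3100 mL, Hct 28%: PVS = (3100 - 2730)/2730 = +13.6%; TBVS = (4306 - 4890)/4890 = -12.0%. This arises because iPV is a flat mL/kg while iTBV is BMI-adjusted, and it needs Day 1 data only.

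**The case against.** The strongest reply is that the intent can be recovered. SAP 7.7.1 repeatedly names the plasma and blood volume indices side by side, and the comparator text looks as if the mention of TBVS was dropped once and mistyped once. Read one index at a time, the arms are disjoint. That is plausible and is the analysis recommended below, but the SAP does not state it.

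Other replies carry weight:
- Overlap is not automatic. If red-cell volume were constant and measured without error, TBV would always move with PV. In the high example, red-cell volume goes from 6000 - 3600 = 2400 mL to 5794 - 3650 = 2144 mL, a fall of 10.7%. Overlap therefore needs real red-cell change or measurement error, and the documents quantify neither.
- SAP 7.1 declares all p-values descriptive, and these comparisons are not among the objectives in SAP 1.1 or protocol 4.2.
- SAP 8 already says the measured indices define low, normal and high status, so only the direction of change still needs that label.

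A reader might infer that a patient who enters both the high and the low comparison also breaks the independence assumption. That does not follow: they are separate tests. It is a contradictory classification and no more.

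**Conclusion.** The arm definitions are wrong as written: they are not mutually exclusive, they are selected on different indices, and no other section resolves it. Overlap between arms requires a Day 3 hematocrit that differs from Day 1; the contradictory Day 1 classification does not.

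The range of roughly 1% to 10% of eligible patients is an illustration from assumed spreads, not an estimate for this trial. A reader might infer that the result would be uninterpretable or that false positives would rise. Neither is supported. The number of shared patients is probably small, and sharing dilutes the contrast and makes the test conservative (with no true difference, in the illustration above). No conclusion on safety or marker stability depends on these tests. Severity: minor.

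**What to change.** Restate the two comparisons as four, each on one measured index for both the Day 1 level and the direction of change:

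- mPVS above +10%: mPVS falling versus rising.
- mTBVS above +10%: mTBVS falling versus rising.
- mPVS below -10%: mPVS rising versus falling.
- mTBVS below -10%: mTBVS rising versus falling.

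Replace BCS with TBVS. Assign zero change to one side; SAP 7.7.1 already splits the mGFR and eGFR changes at below zero versus zero or above, and the same split would serve. Reconcile SAP 4.3.2 on hematocrit with protocol Table 7 and with the SAP's own plan for mTBV on both days.

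Arm overlap is then zero by construction, and no patient can be both high and low on one index. A patient discordant between indices may still appear in a high analysis of one and a low analysis of the other, but each is labelled by its index. The cost is SAP wording and two more descriptive comparisons; no new data are needed.

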Cohort 1 used FD003 to monitor a change in volume induced by the infusion of 350 ml of 5% albumin solution given over 30 minutes. At 5 minutes post completion of the infusion, the average plasma volume increase was 324 ml with an SD of 49mL, showing excellent accuracy for following a change in plasma volume. By 30 minutes post infusion, the average volume increase from baseline was reduced to 224ml showing that FD003 was being retained within the vasculature even though the 5% Albumin solution was slowly distributing into the interstitial space. This cohort was not used for PK due to the complication of accounting for the additional volume infused.

The FAST VFI was generally safe and well tolerated in healthy patients in Cohorts 1 and 2 and in patients with impaired renal function in Cohorts 3 and 4. No severe or serious TEAEs, TEAEs leading to study drug discontinuation, or deaths were reported during the study. Overall, the majority of TEAEs reported were mild in severity. Three patients in Cohort 4 had a TEAE of blood creatine phosphokinase increased related to clinically significant abnormal creatine kinase levels. All 3 TEAEs of blood creatine phosphokinase increased were mild in severity and considered by the investigator to be possibly related to study drug. There were no other clinically significant abnormal clinical laboratory values. There were no clinically significant abnormal ECG or vital signs measurements, nor were there clinically meaningful trends identified in observed values or changes from baseline. There were no clinically significant abnormal physical examination findings.

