## 7.2 Derived Parameters

The following formulas will be used for determination of estimated and measured TBV, ideal TBV, estimated and measured total blood volume status (eTBVS and mTBVS), ePV, estimated PV change, ideal PV, estimated and measured plasma volume status (ePVS and mPVS), and eGFR on day 1 and day 3:

Nadler formula for eTBV (Sharma & Sharma, 2020):

- Men:  $eTBV [L] = (0.3669 \times \text{Height [m]}^3) + (0.03219 \times \text{Weight [kg]}) + 0.6041$
- Women:  $eTBV [L] = (0.3561 \times \text{Height [m]}^3) + (0.03308 \times \text{Weight [kg]}) + 0.1833$

mTBV will be calculated as follows:

- $mTBV [mL] = mPV [mL] / (1 - \text{hematocrit [\%]} / 100)$

Lemmens-Bernstein-Brodsky formula for ideal TBV (iTBV) (Lemmens, Bernstein, & Brodsky, 2006):

- $iTBV [mL/kg] = 70 / [\text{sqrt}(\text{body mass index}/22)]$  – the lowest body weight during the days 1 to 5 will be used for calculation of BMI
- $iTBV [mL] = iTBV [ml/kg] \times \text{weight [kg]}$  – the lowest body weight during the days 1 to 5 will be used for calculation

Estimated and measured total blood volume status:

- $eTBVS [\%] = \text{Percentage change from iTBV: } (eTBV - iTBV) / iTBV$
- $mTBVS [\%] = \text{Percentage change from iTBV: } (mTBV - iTBV) / iTBV$

Kaplan-Hakim Formula for ePV (Ling et al., 2015):

- Men:  $ePV [mL] = (1 - \text{hematocrit [\%]}) \times [1530 + (41 \times \text{weight [kg]})]$
- Women:  $ePV [mL] = (1 - \text{hematocrit [\%]}) \times [864 + (47.9 \times \text{weight [kg]})]$

Strauss formula for plasma volume change (Strauss, Davis, Rosenbaum, & Rossmeis, 1951):

- $PV\_2/PV\_1 \times 100 [\%] = \text{hemoglobin\_1 [g/dL]} / \text{hemoglobin\_2 [g/dL]} \times (1 - \text{hematocrit\_2 [\%]}) / (1 - \text{hematocrit\_1 [\%]}) \times 100$

Plasma volume change will also be calculated via the ratios of ePV by the Kaplan-Hakim-Formula

Harrison formula for ideal PV (iPV) (from Ling 2015):

- Men: iPV [mL] = 39 [mL/kg] × weight [kg] – the lowest body weight during the days 1 to 5 will be used for calculation
- Women: iPV [mL] = 40 [mL/kg] × weight [kg] – the lowest body weight during the days 1 to 5 will be used for calculation

Estimated and measured plasma volume status (ePVS and mPVS):

- ePVS [%] = Percentage change from iPV: (ePV - iPV)/iPV
- mPVS [%] = Percentage change from iPV: (mPV - iPV)/iPV

The eGFR will be calculated using CKD-EPI formula (Levey et al., 2009):

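### SAP 7.7.1 compares patients by the sign of their volume or mGFR change, with no unchanged group and no continuous analysis alongside (minor)

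*SAP*

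**What the plan says.** SAP 7.7.1 Efficacy contains two kinds of direction comparison.

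- **By volume direction.** Among patients with high Day 1 PVS or TBVS (above +10%), percentage mGFR change in those whose status falls is "compared to patients with a high PVS or TBVS and an increasing PVS between Day 1 and 3". Among those with low status (below -10%) the SAP asks whether patients with "an increasing PVS or TBVS between Day 1 and 3 had significantly different percentage change of mGFR" from patients whose status falls. The test is a t-test or Mann-Whitney test. The comparator is worded with PVS alone although the first group is worded with either measure.
- **By mGFR direction.** The SAP asks whether "patients with an improving (i.e. increasing) mGFR from day 1 to day 3 differ significantly from patients with a worsening (i.e. decreasing) mGFR" in baseline characteristics, volume status and remaining length of stay.

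Neither names a minimum change, an unchanged category or a continuous counterpart. Nearby text does. The model introduced by "To evaluate whether the percentage changes of mGFR from day 1 to day 3" uses that change both cut at zero and as a continuous variable, and the mGFR/eGFR ratio is analysed with two cut-offs and also continuously. The analysis of physician disagreement states: "A measured change in TBVS of more than 5% between Day 1 and 3 was determined as a significant change". No such threshold exists for PVS or mGFR. For the agreement of estimated and measured volume change the SAP says "These plots will be analysed exploratory, since no appropriate values for limits of agreements are available".

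SAP 7.1 declares all p values descriptive and hypothesis-generating.

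**The concern.** A sign split treats a patient whose volume moves by a fraction of a percent like one who moves by 20%, and it forces a direction on a patient who has not changed. With at most 50 patients, divided first by Day 1 status and then by direction, the comparison discards much of what was measured.

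There is a second problem. The Day 1 reading both admits the patient to the high or low group and serves as the reference for change. A patient admitted partly because of a chance high reading will tend to read lower on Day 3. The two direction groups are then not simply patients who lost and patients who gained volume.

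At stake is whether these analyses can do the job SAP 7.1 gives them, which is to suggest hypotheses for later trials. SAP 7.7.1 models volume change against length of stay, dialysis, rehospitalization and mortality, but relates it to mGFR change only through the sign split.

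**Working it through.** The SAP states no power, effect size or measurement error for these comparisons, so there is no figure to reproduce. The sizes below are illustrations on stated assumptions.

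**1. What the sign depends on.** Ideal PV uses one weight for both days (SAP 7.2: "the lowest body weight during the days 1 to 5 will be used for calculation"). So change in mPVS = (mPV Day 3 - mPV Day 1) / iPV, and its sign is the sign of the mPV change. Likewise, the sign of the mTBVS change is that of mTBV.

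**2. Cost of the split.** Assumed: 25 high patients; true change in status with mean 0 and SD 8 points; error SD 5 points in the measured change; residual SD of mGFR change 20%; two-sided 5% level. The slope is in points of mGFR change per point of volume change. Simulated power:

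| Error SD | Slope | Sign split | Continuous | Ratio |
|---|---|---|---|---|
| 5 points | 0.8 | 17% | 24% | 17/24 = 0.71 |
| 5 points | 1.2 | 29% | 45% | 29/45 = 0.64 |
| none | 0.8 | 22% | 31% | 22/31 = 0.71 |
| none | 1.2 | 42% | 58% | 42/58 = 0.72 |

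Repeat runs move these by a point or two, up to three in the last row. The ratio barely depends on the error. The gap is therefore mainly the ordinary cost of dichotomising; error lowers power for both methods.

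**3. Wrong direction for small true changes.** For error CV c per reading, the SD of the change is s = c x sqrt(2). For a true change d, and before any selection on Day 1, P(wrong sign) = Phi(-d/s).
- c = 2%: s = 2.83. For d = 2, Phi(-0.71) = 24%; for d = 5, Phi(-1.77) = 4%.
- c = 5%: s = 7.07. For d = 2, Phi(-0.28) = 39%; for d = 5, Phi(-0.71) = 24%.

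**4. Tilt from selecting on Day 1.** Simulated with assumed true status mean +10%, SD 15%, CV 2-7%.
- No true change: 53-61% of high patients are labelled decreasing and 56-69% of low patients increasing.
- True change SD 5-8 points, mean 0: 13-37% of high patients carry the wrong direction.
- Every patient truly falling by 5 points: 76-94% of high patients are labelled decreasing, so 6-24% are wrong.

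**5. Which CVs are plausible.** The documents give no repeatability across two doses. Their only figure for variability of PV change is in Protocol 3.1.3.4: "the average plasma volume increase was 324 ml with an SD of 49mL", after an albumin infusion and within one dose. For an assumed PV of 4000 to 2500 mL this is 49/4000 = 1.2% to 49/2500 = 2.0%. It is the SD of a change, so it compares with s; dividing by sqrt(2) gives about 0.9-1.4% per reading. It omits error that differs between doses. It supports the low end of the assumed range better than the high end.

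**6. Shared error.** Protocol 3.1.2 says GFR is obtained from FD001 decline together with the measured PV. If PV error carries into mGFR (assumed error correlation 0.3-0.6, CV 5-10% for both), high patients with no true change show a spurious difference of about 3 to 13 percentage points in mGFR change between direction groups. These CVs lie above what step 5 supports.

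**7. Would the 5% rule help?** Read as 5 points, the share of unchanged patients still given a direction is 2 x Phi(-5/s) instead of 100%: 8% (c = 2%), 24% (3%), 48% (5%), 72% (10%). It helps only if error is small.

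**The case against.** Four objections carry weight.

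- **Noise is not the main cause of the power loss.** A reader might infer that measurement error at the zero cut is what costs power. Step 2 shows otherwise: the gap persists with no error at all.
- **Unchanged patients are not the typical case.** These are decompensated patients under active fluid management. Where most truly lose volume, most labels are right, as the uniform 5-point fall shows. The 53-61% figure is a limiting case.
- **The 5% rule is not a general standard that the SAP breaks.** It might be read that way, but it sits in the physician-disagreement analysis, where the survey offers no change as a third answer and a band is needed to match it. It covers TBVS only and is not presented as a measurement-error limit.
- **Not every unchanged patient is assigned a group.** That is true of the mGFR split. Patients within 10% of ideal on Day 1 enter neither volume comparison; in simulations with assumed true PVS mean 0 or +10%, SD 15-20% and CV 3-10%, they are 31-49% of patients.

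The stakes are also low. These comparisons are not among the objectives in SAP 1.1, their p values are descriptive, and no primary endpoint rests on them. All of this stands. It limits the size of the point but does not supply the missing continuous analysis.

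**Conclusion.** The point holds as a minor one. On the plain reading, the volume-direction and mGFR-direction comparisons are cuts at zero with no unchanged group and no continuous version, unlike neighbouring analyses in the same section. The firm part is the loss of information from dichotomising: roughly 30% of the power in the illustration, with or without measurement error. That proportion rests on the assumed normal changes and linear relation. The tilt from selecting on Day 1 is real in direction, but its size depends on CVs that the documents do not give and that their one related figure places towards the low end.

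The documents do not support saying that the groups are mostly random or that these analyses are invalid.

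**What to change.** In SAP 7.7.1:

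1. Make the main analysis a linear regression of percentage mGFR change on the continuous Day 1 to Day 3 change in mPVS, and separately in mTBVS, adjusted for the Day 1 value. Use all patients with both measurements, and optionally repeat within the high and low groups. Separate models also remove the mixed PVS/TBVS wording of the comparators.
2. Relate baseline characteristics, volume status and remaining length of stay to continuous percentage mGFR change, by regression or Spearman correlation.
3. State the caveat that mGFR is computed from measured PV, so shared error can bias these associations. The continuous model does not remove this.
4. Keep direction groups for display only. If an unchanged band is shown, the existing 5% rule may serve for TBVS, once the SAP says whether it means percentage points or relative change. A band for PVS or mGFR needs its own justification.

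The cost is SAP wording and a few lines of code; no new data are needed. The regression brings a linearity assumption, which a scatter plot can check, and a display band makes the direction groups smaller.
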